Any SAE will be brought to the attention of the PIs and the study physician as soon as possible and not longer than 24 hours. Any AE or SAE that is both unexpected and related to study participation will be reported to the IRB within 7 days of the event. The IRB will make a determination as to whether additional reporting requirements are needed. IRB actions will be reported to the funding agency by the PIs no less than annually and more frequently as recommended by the local IRB. Any SAEs will be summarized in the yearly Progress Reports to the funding agency, including a review of frequency and severity. All SAEs will be followed through ongoing consultation with the physician caring for the patient until they resolve, result in death, or stabilize and are not expected to improve. The study staff will be in close contact with participants and health care providers throughout the study to monitor for potential unanticipated problems. Any unanticipated problems will be discussed at the weekly research staff meetings and reported as required to the CHRMS using the Report of Protocol-Related Problems & Deviations Form.

Withdrawal Procedures: Define the precise criteria for withdrawing subjects from the study. Include a description of study requirements for when a subject withdraws him or herself from the study (if applicable).

There are no predefined criteria for withdrawal from the study. However, participants may be withdrawn if the PI determines it is not advisable that they continue on in the program. Participants may withdraw themselves at any time, for any reason.

Sources of Materials: Identify sources of research material obtained from individually identifiable human subjects in the form of specimens, records or data. Indicate whether the material or data will be obtained specifically for research purposes or whether use will be made of existing specimens, records or data.

Sources of material will include:

- Questionnaires on demographics (age, marital status, education, etc.) and physical and mental health
- Questionnaires about cigarette use, withdrawal and cravings, as well as thoughts and feelings about smoking
- Urine and breath samples that measure recent cigarette use and exposure to tobacco byproducts
- Questionnaires about the time and effort required to attend study-related visits
- Tasks that measure the value of cigarettes and the strength of preference for money available now compared to money available later

DRUG INFORMATION

Investigators are encouraged to consult the UVM Medical Center Investigational Pharmacy Drug Service ([name]) prior to finalizing study drug/substance procedures.

Drug (s)

Not applicable

Drug name – generic followed by brand name and common abbreviations. Availability – Source and pharmacology; vial or product sizes and supplier. If a placebo will be used, identify its contents and source.

Preparation: Reconstitution instructions; preparation of a sterile product, compounded dosage form; mixing guidelines, including fluid and volume required. Identify who will prepare.

Storage and stability – for both intact and mixed products.

Administration – Describe acceptable routes and methods of administration and any associated risks of administration.

Toxicity – Accurate but concise listings of major toxicities. Rare toxicities, which may be severe, should be included by indicated incidence. Also adverse interactions with other drugs used in the protocol regimen as well as specific foods should be noted. Address significant drug or drug/food interactions in the consent form as well. List all with above details.

Is it FDA approved: (include FDA IND Number)

1. in the dosage form specified? If no, provide justification for proposed use and source of the study drug in that form.
2. for the route of administration specified? If no, provide justification for route and describe the method to accomplish.
3. for the intended action?

SUBJECT CHARACTERISTICS, IDENTIFICATION AND RECRUITMENT

Subject Selection: Provide rationale for subject selection in terms of the scientific objectives and proposed study design.

Despite widespread awareness of the adverse health consequences of SHSe, almost 60% of all U.S. children and 85% of those from low-income families are chronically exposed (Cornelius et al., 2003; Halterman et al., 2010; USDHHS, 2007). SHSe, especially from maternal smoking, increases risk for infant death, chronic respiratory infections, asthma, and other longer-term medical problems. Thus, studying potential treatment approaches to reduce maternal smoking in disadvantaged populations is of the utmost importance.

Vulnerable Populations: Explain the rationale for involvement of subjects (e.g., cognitively impaired, Non-English speaking, prisoners, students). Discuss what procedures or practices will be used in the protocol to minimize their susceptibility to undue influences and unnecessary risk (physical, psychological, etc.).

Not applicable

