Primary aim # 2: determine whether maternal smoking cessation decreases objective measures of SHSe in children. Urine samples will be collected from the youngest child of each maternal participant at each follow-up assessment for determination of cotinine levels. We will examine this outcome by (a) comparing between treatment conditions and (b) comparing children of abstainers versus smokers independent of treatment condition. We hypothesize that (a) both incentives interventions will decrease child cotinine levels significantly more than usual care alone and (b) that SHSe levels will be significantly lower among children of abstainers than smokers.

Secondary aim: utilize behavioral-economic measures to improve understanding of treatment process and predict outcomes. Women will complete smoking-price sensitivity and delay-discounting tasks at study intake and follow-up assessments. We hypothesize that cigarette price sensitivity will increase as an orderly function of treatment intensity and differ between treatment conditions, and that steeper baseline discounting (i.e., greater impulsivity) will predict smoking abstinence at follow- up assessments after controlling for the influence of treatment.

METHODS AND PROCEDURES

Study Design: Describe the research design, including a description of any new methodology and its advantage over existing methodologies.

This study is a randomized clinical trial with three treatment conditions. Treatment conditions will last for 12 weeks and consist of either **A**: usual care for reducing SHSe. **B**: provisions of incentives contingent upon biochemically-verified maternal smoking abstinence or **C**: the incentive program combined with provision of and support in using of pharmacotherapies. Outcome measures will include maternal abstinence rates, child cotinine exposure and the interaction of behavioral economic measures and treatment success. This extended treatment period of combined incentive and pharmacotherapy support represents a novel and intense approach to reducing smoking and second-hand smoke exposure in these vulnerable populations.

Procedures: Describe all procedures (sequentially) to which human participants will be subjected. Identify all procedures that are considered experimental and/or procedures performed exclusively for research purposes. Describe the types, frequency and duration of tests, study visits, interviews, questionnaires, etc.

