Usual care. The 2008 Clinical Practice Guidelines for smoking cessation recommends that medical providers should at a minimum implement the 5As (Fiore et al., 2008). To assure that referring pediatric services are at least acquainted with the 5As, our staff will conduct office-based training sessions with all referring practices prior to the start of study recruitment and once annually throughout the course of the study using training procedures developed previously by our research team and utilized in our prior studies. As part of training in the 5As, providers will be encouraged to refer smokers to the Vermont Quit Network that is supported by the Vermont Department of Health (<http://www.vtquitnetwork.org>). This network offers a wide range of free cessation services, including nicotine replacement therapy wherein free nicotine patches, gum, or lozenges will be mailed directly to the participant's home. There are basic web-based modules on preparing to quit, motivating oneself during the quit process, a review of the reasons that people smoke, evaluating whether pharmacotherapy may help, developing a quit plan, and sustaining abstinence. Additionally, they provide free online coaching that includes forums with former smokers and others who are currently trying to quit, or individual smoking-cessation phone counseling, or in-person smoking-cessation group counseling offered in the local community hospitals. Importantly, we will have no involvement with the content of counseling or other smoking-cessation services that might be routinely offered through the referring medical practices aside from us providing the once yearly workshop on how to implement the 5As and recommending them to refer women to the Vermont Quit Network. Our goal is for this condition to represent usual care and not standard of care as stipulated in the Clinical Practice Guidelines. As discussed above in the section on follow-up assessments, we will assess all mothers on smoking-cessation recommendations and services received through their children's health-care providers, which is information that can be considered in cost-effectiveness and other analyses.

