The assessment battery will be completed with all mothers and children again at 6, 12, 24, and 48 wks after intake by staff blind to treatment condition. All subjects will be compensated \$35 per follow-up assessment independent of smoking status to assure high compliance. We have achieved high rates of follow-up compliance (85-90%) in prior studies with this level of compensation and anticipate the same in the proposed study. Urine specimens collected from mothers and children at the follow-up assessments will be sent to an outside laboratory for cotinine testing using gas chromatography (GC) with maternal and liquid chromatography-mass spectrometry (LC-MS/MS) for child specimens; maternal specimens will also be assessed for tobacco alkaloids anabasine and anatabine using LC-MS/MS to discriminate between cotinine from smoking vs. NRT use (Jacob et al., 2002). Participants will complete a brief yes-no questionnaire consisting of five questions adapted from prior studies with women on smoking-cessation services received (e.g., Sherman et al., 2005): (1) Has your child's doctor talked with you about smoking cessation since last assessment? (2) Has your child's doctor referred you to a smoking-cessation clinic or related service (e.g., online/phone counseling) since last assessment? (3) Have you attended a smoking-cessation clinic (or online or phone counseling) since last assessment? (4) Has your child's doctor recommended or prescribed a smoking-cessation medication (e.g., nicotine patch/gum/lozenges, Zyban) since last assessment? (5) Have you used any smoking-cessation medications since last assessment? Those reporting use of a pharmacotherapy will complete a TLFB interview to characterize use since last assessment.

Importantly, in an effort to minimize physical contact between research personnel and existing participants in light of the COVID-19 pandemic, we will be conducting follow-up surveys over the phone. Additionally, video monitoring will be used to verify the smoking status of the mothers. This procedure involves video chatting with participants to monitor them as they self-test saliva samples for cotinine (i.e., a metabolite of nicotine) using Alere iScreen OFD Oral Cotinine Screening tests. Participants will video chat with research personnel while completing the tests, with each test taking approximately 5 minutes (i.e., 2-3 minutes of swabbing the mouth and tongue, and up to 3 minutes

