
Economic Evaluation, Cost analysis.

We will conduct a cost-effectiveness analysis (CEA) from the societal perspective (Drummond et al., 2005). First, to determine

the cost of each intervention, we will employ the Brief Drug Abuse Treatment Cost Analysis Program (Brief DATCAP; French et al., 2004), which has been widely used in the area of substance abuse (e.g., French et al., 2008; Roebuck et al., 2003; 2009; 2011; <http://datcap.com/>), including incentives projects (Knealing et al., 2008). The economic cost of treatment will be derived by allocating fixed costs based upon the proportion of time or space utilized by the programs and costs that vary by patient engagement and smoking status (e.g., drug tests, financial incentives). The total cost per treatment episode will be individual-specific, and will also include the opportunity cost of the patient's time while in treatment as measured by the Client (Outpatient) version of the DATCAP (French 2005; Salomé et al., 2003). The time period of the cost analysis will span from intake to discontinuation or completion of the program. The cost of all research-specific resources consumed will be excluded from the evaluation. All costs and benefits will be expressed in a common dollar year. Estimated treatment costs will be combined with the estimated child healthcare utilization costs to represent total costs per treatment condition. Cost-effectiveness analysis. CEA will be conducted wherein the average (mean) difference in treatment costs across the three treatment conditions will be divided by the average (mean) difference in each outcome to derive incremental cost-effectiveness ratios (ICERs). Statistical significance of these ICERs will be determined by employing non-parametric bootstrapped standard errors (Drummond et al., 2005). A special form of CEA, cost-utility analysis (CUA), will be performed. Based upon smoking status from the quit date through the 48-week assessment, the number of quality-adjusted life years (QALYs) gained by the mother—as measured by the proportion of time spent in 'smoking' and/or 'non-smoking' status will be derived using QALY weights recommended in the extant literature (e.g., Cromwell et al., 1997; Flack et al., 2007). We will estimate relapse curves beyond the 48-week assessment from the literature to estimate longer-term outcomes. QALYs gained by each child based on changes in their biochemically verified SHSe will be similarly calculated using QALY weights recommended in the literature (Taylor, 2009). The incremental cost per QALY gained between the three treatment conditions will be calculated and compared for mothers and children separately and also summed across mothers and children. In conducting analyses for children, we will assume that all children residing fulltime with the mother share the same smoking status as the target child.

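### Maternal cessation costs stop when a woman leaves or finishes the 12-week programme, while her QALYs run to week 48 and beyond, so outside cessation services used later are not in the incremental cost

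*Protocol*

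**What the plan says.** Everything needed to see the mismatch is in the Protocol, mostly under Economic Evaluation, Cost analysis.

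- Perspective: "We will conduct a cost-effectiveness analysis (CEA) from the societal perspective".
- Cost window: "The time period of the cost analysis will span from intake to discontinuation or completion of the program". Study Design gives the programme length: "Treatment conditions will last for 12 weeks".
- Effect window: maternal QALYs are derived "Based upon smoking status from the quit date through the 48-week assessment", and then "We will estimate relapse curves beyond the 48-week assessment from the literature to estimate longer-term outcomes".
- ICER numerator: "the average (mean) difference in treatment costs across the three treatment conditions will be divided by the average (mean) difference in each outcome". The same section also defines a wider total, which adds child healthcare utilisation to treatment cost. Health record review takes the child's records, where the mother permits it, to 48 weeks after the quit date.
- Data on later services: Follow-up Assessments has yes/no questions at weeks 6, 12, 24 and 48 on counselling attended and medication used, and adds "Those reporting use of a pharmacotherapy will complete a TLFB interview to characterize use since last assessment". The Usual care text says of the services information only that it is something "which is information that can be considered in cost-effectiveness and other analyses".
- Analysis set: Statistical Considerations keeps all randomised women in the primary analyses whatever their compliance or dropout, and Study Populations in the SAP does likewise.

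The SAP has no economic section, so it neither changes nor completes the rule.

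**The concern.** A societal analysis should count the resources that produced the effects it credits. Here costs are cut at an event that happens after randomisation, while effects continue. Suppose a woman leaves the incentive programme early, later uses free counselling and nicotine replacement from the state quit network, and is abstinent at week 24 or 48. Her abstinence and QALYs count for her arm, but only the cost up to her departure does. A completer who uses the same services after week 12 raises the same problem.

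Such use is foreseeable. Referring practices are encouraged to send women to the network, its contact details are in the consent form, and the incentives-only arm may use medication from any source. A difference between arms is possible too, because staff register consenting women with the network only in the pharmacotherapy arm.

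Cost-effectiveness belongs to primary aim 1, which predicts that incentives plus pharmacotherapy will be the most cost-effective option. The two incentive arms share one payment schedule, so their cost difference is probably smaller than either arm's difference from usual care. An omitted service cost could weigh more in that comparison. The abstinence endpoints themselves are not affected.

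**Working it through.** **Step 1. Reproduce the plan's cost figure.** The documents state no ICER or total cost. The main in-window figure is the incentive maximum.
- Visits (Abstinence-monitoring schedule): 5 + 7×2 + 4×1 = 23, matching the 23 under Compensation.
- Payment at the k-th consecutive negative test: min(50, 10 + 2.5(k - 1)), which reaches $50 at k = 17.
- Sum: 17 × (10 + 50)/2 + 6 × 50 = 510 + 300 = $810, as stated.
- Expected earnings: 0.40 × 810 = $324, as stated.

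**Step 2. Compare the windows.**
- Completer: about 12 of 48 weeks fall inside the maternal cost window, so 36/48 = 75% of the within-trial QALY period carries no maternal cessation cost.
- A woman leaving at week 4 (assumed): 44/48 = 92%.
- After week 48, QALYs are extrapolated and no rule for cessation costs is given.

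**Step 3. See who is affected.** Under the SAP's Missing Data rule, a woman with missing smoking status counts as a smoker. The mismatch therefore concerns women who leave the programme but attend later assessments, and completers who use services after week 12. Week-12 results for completers are largely untouched.

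**Step 4. Illustrate the size.** The documents give neither unit costs nor rates of later use, so both inputs here are assumptions. Let d be the between-arm difference in the proportion of women using later services, and c the cost per user. The shift in incremental cost per woman is d × c.
- d = 0: $0, whatever c is.
- d = ±0.05, c = $100: ±$5.
- d = ±0.20, c = $300: ±$60.

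For scale against usual care, use the planned week-24 difference of 15 points (20% vs 5%).
- Incentive payments per extra abstainer: 324/0.15 = $2,160.
- Largest shift per extra abstainer: 60/0.15 = $400, and 400/2,160 = 18.5%.

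The base is payments only. Fixed costs, testing and patient time would enlarge it and shrink the percentage. With c raised to $500, the limit becomes ±0.20 × 500 = ±$100 per woman, or 31% of $324. The answer is set by the assumption.

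**Step 5. Apply the plan's own expectation.** The Protocol expects under 10% ongoing pharmacotherapy use in the usual-care and incentives-only arms. If that carried over after the programme, medication use in those two arms could differ by at most 10 points: 0.10 × 300 = $30 per woman, 30/0.15 = $200 per extra abstainer, and 200/2,160 = 9.3%. This bound is partial. It does not cover counselling or the pharmacotherapy arm, and it is not stated as a rate after the programme.

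**The case against.** The best defence is that the sentence simply sets the window for costing the programme. A 12-week programme has no programme costs after week 12, and short costs with longer effects are normal for a time-limited intervention. That is right for programme resources. It does not answer for outside cessation services under a declared societal perspective.

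Four stronger readings are tempting, and the documents do not support them.

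- *That weeks 12 to 48 are wholly uncosted.* Child healthcare utilisation is added to total cost and may run to week 48. Only maternal cessation costs are missing.
- *That usual care has no programme to finish, so the window differs by arm.* Study Design and the SAP give every condition 12 weeks, and the abstinence-monitoring schedule applies to all mothers. Outside services can be used later in any arm.
- *That the rule excludes the later services data.* The Usual care text expressly allows the services information to be considered. But it sets no window, unit costs or commitment, so the stated cost window is left as it stands.
- *That the bias favours a particular arm or has a known size.* Nothing in the documents gives later use by arm. A range that omits zero or shows one sign only would mislead.

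**Conclusion.** The point holds in a limited form. As written, maternal cessation costs end no later than about week 12, while the effects credited to the same women run to week 48 and beyond. Outside services used in between are left out of the incremental cost in all three arms. The consequence falls mainly on the 24- and 48-week outcomes, the QALYs and women who discontinue, and it reaches an ICER only if later use differs between arms.

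The direction is unknown. Over the assumed ranges the shift lies between -$60 and +$60 per woman, with zero a real possibility. The low medication use expected in two arms makes the smaller end more likely. These figures illustrate the mechanism and do not forecast it. A correction is still worth making, because cost-effectiveness is part of a primary aim and the data are already planned. Separately, the two descriptions of the numerator, treatment cost alone and treatment plus child healthcare, need to be reconciled.

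**What to change.** Replace the window sentence in the Protocol and add a short economic section to the SAP that does four things.

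1. Counts cessation-related costs from intake to week 48 for every randomised woman, whatever her programme status, by applying unit costs to the services questionnaire and the medication timeline.
2. Uses one numerator in the within-trial ICERs: treatment cost, plus later cessation services, plus child healthcare.
3. States what is assumed about cessation costs in the period extrapolated beyond week 48.
4. Reports the programme-only window as a sensitivity analysis.

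The cost is wording and unit-cost look-ups, with no new data collection. The one weakness is that counselling is recorded only as yes or no, so its intensity must be assumed and varied.
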